1.0 Objectives

1.1 Study Objectives

Our long term goal is to understand the likely health effects of cigarette smokers switching to a Standardized Research E-Cig (SREC) and to assess the role of nicotine delivery on switching, acceptability and markers of health outcomes. The specific objective of this proposal is to recruit a cohort of 240 current exclusive daily cigarette smokers and to measure a comprehensive battery of health markers at baseline and at 3 and 6 weeks after attempting to switch completely to SRECs containing either zero or 58 mg/ml nicotine in a randomized double-blind, placebo-controlled design with the following three specific aims:

- **1.1.1** Aim 1: To characterize the short-term effects of attempting to switch from traditional cigarette smoking to a Standardized Research E-Cig from baseline to 6 weeks using a comprehensive battery of measures (e.g. carcinogen biomarker (NNAL), pulmonary function testing, Holter EKG, exhaled CO, and cotinine, BP etc.).
 - **1.1.1.1** Our hypothesis is that attempting to switch to a SREC will result in a reduction in markers of harms to health, as compared with the baseline (exclusive cigarette smoking) measures.
- **1.1.2** Aim 2: To compare the effects of switching to a standardized research electronic cigarette (SREC) with pods containing 58 mg/ml nicotine liquid versus 0 mg/ml nicotine liquid on smoking behavior and changes in health markers at 6 weeks post-switching.
 - **1.1.2.1** Our hypothesis is that nicotine-containing SRECs will facilitate switching from smoking more efficiently than zero nicotine SRECs and will result in a significantly greater improvement in markers of health risk, but will conversely result in higher ratings of dependence on the SREC (as compared to the zero nicotine SREC) at 6 weeks post-switching (after controlling for baseline measures).
 - **1.1.2.2** We also hypothesize that the nicotine-containing SRECs, (as compared with the zero nicotine SRECs, after controlling for baseline) will result in a lower total score for the withdrawal items on the MNWS and lower mean scores on ratings of cigarette craving, during the first week of the trial.

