1.3 Secondary Study Endpoints

Secondary outcomes for the study include changes in pulmonary function (FEV-1), tobacco-related toxicant concentrations, such as exhaled CO, EKG markers (HRV, PVCS, ST elevations, WRS duration),

urine cotinine, and blood pressure at 6 weeks, controlling for baseline measures. In addition, nicotine withdrawal and cravings, measured on the MNWS, at 1 week controlling for baseline. Finally, the average number of cigarettes smoked per day (CPD) and measures of dependence (e.g. FTND, PSECDI) will be analyzed. Outcomes at the 10 week telephone follow-up include the average number of cigarettes smoked per day in the week prior to the follow-up call, the number of days on which an e-cig was used in the previous 21 days, and the self-reported cigarette abstinence (zero cigarettes smoked in the prior week).

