- **7.2.2.7** Following randomization, participants will receive the assigned study product (SREC with 0 mg/ml nicotine liquid or SREC with 58 mg/ml nicotine liquid; researcher and subject are blind to the nicotine dose), which will be pre-prepared by the unblinded research staff.
 - **7.2.2.7.1** Participants will be provided 2 rechargeable e-cig batteries, 1 wall adapter, 1 USB charger cord, a user manual, and a supply of pods, based on the participant's cigarette smoking (up to 22 pods). In a case where the participant will run out of pods, the participant will be able to come to the study to pick up an additional supply.
 - **7.2.2.7.2** Research staff will then explain how to use the device.
 - **7.2.2.7.3** Participants will be advised to cease all tobacco use and to start using their assigned e-cig product beginning the next morning.
 - **7.2.2.7.4** Participants will be provided with smoking cessation resources that are available in the community, and they will be encouraged to use them. In

addition, participants will be given the document from the Centers for Disease Control and Prevention titled, "A Report of the Surgeon General: How Tobacco Smoke Causes Disease."

- 7.2.2.7.5
- 7.2.2.7.6 Participants will be instructed to complete daily diaries related to their study product and cigarette use (E-cigarette Daily Diary includes place to record cigarette use as well). They will also be asked to return all used or unused e-cig pods at their next study visit.
- 7.2.2.7.7 Pulmonary Function Testing (PFTs) PFTs will be conducted as described in the Time and Events Table at Visits 1, 2, and 3. Any significant worsening (10% worsening or greater) in pulmonary function will be documented as an adverse event. All adverse events will be documented and reviewed by the Medical Monitor within 5 business days. In cases where the medical monitor suspects that a participant may be having a respiratory adverse event related to the study, a pulmonologist ([name]) will be consulted. The pulmonologist will make any needed medical recommendations and a determination regarding whether the participant is able to continue with the study.

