 - **7.2.2.7.7.1** When COVID protocols apply: The researcher will then leave the clinic space to complete the pulmonary function test, as the participant will need to remove their mask for this test. This will be facilitated by a two-way mirror and an intercom system. The researcher will remain outside of the clinic space for 15 minutes following the completion of this test and will use a timer to ensure that this time restriction is met.
- **7.2.2.8** Upon completion of the PFT test, participants will be given the opportunity to use the SREC device and ask the researcher any questions about its use prior to leaving the visit. The researcher will use the two-way mirror and intercom system to answer any questions.

(Part C): Visit Wrap-Up

- 7.2.2.9 Participants will then be provided with instructions to complete additional measures via a home computer/smart phone (see table of measures). A link to the surveys in REDCap will be sent to the participant's email address or phone. Participants will be instructed to complete all questionnaires within 24 hours. Participants unable to complete the questionnaires at home via a computer/smart phone will be called by the researchers to complete the questionnaires.
- **7.2.2.10** As the participant leaves the clinic space, participants will be provided with the Greenphire ClinCard.
 - **7.2.2.10.1** Once participants complete the additional questionnaires considered to be part of the visit (completed at home within 24 hours), they will be compensated for the visit. The funds will be automatically loaded onto the card.
 - **7.2.2.10.2** Those who do not complete the visit by completing the at-home questionnaires (which includes an option to opt-out of answering) will only be compensated for travel.

7.2.3 Switching Phase –Phone Contact #1 (Day 7 ± 7 days) and Phone Contact #2 (Day 14 ± 7 days) Note: While visit windows were extended to allow the participant flexibility, no visits (in person or phone), will occur on the same day.

During each phone contact, daily study product and cigarette use will be collected, adverse events or changes to concomitant medications will be documented, and participants will be asked to answer the measures indicated in the Time and Events Table. Participants will also be provided with advice/encouragement to remain abstinent from cigarettes. Participant's compensation for completing the phone call will be added to their gift card.

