7.2.4 Switching Phase – Visit 2 (Day 21 ± 7 days)

The following procedures will be completed in a private clinic space in the Clinical Research Center. Participants and researchers will be wearing appropriate PPE at all times, except for noted measures where the participant will need to remove their mask (when COVID protocols apply).

Prior to the visit:

7.2.4.1 Participants will then be provided with instructions to complete measures via a home computer/smart phone (see table of measures). A link to the surveys in REDCap will be sent to the participant's email address or phone the day of the clinic visit. Participants will be instructed to complete all questionnaires within 24 hours. Participants unable to complete the questionnaires at home via a computer/smart phone will be called by the researchers to complete the questionnaires.

(Part A): Participant Check-In

7.2.4.2 The following measures will be completed:

- **7.2.4.2.1** Adverse events will be documented, and any concomitant medication changes will be recorded.
- **7.2.4.2.2** The cigarette and study product use diary will be collected by the researcher and entered into Daily Cigarette and E-cig Use Diary Log in Redcap.
- **7.2.4.2.3** Use of other tobacco products in the past 7 days will be assessed via the Other Tobacco Use form.
- **7.2.4.2.4** Participants will be encouraged to remain abstinent from cigarettes.
- **7.2.4.2.5** Participants will be instructed to complete daily diaries related to their study product and cigarette use (E-cigarette Daily Diary). They will also be asked to return all used and unused e-cig pods at their next study visit.
- **7.2.4.2.6** Participants will be provided with a supply of pods based on their usage.

(Part B): Completion of Biomeasures

- **7.2.4.3** The participant will then leave the clinic space to have their blood pressure and weight measured.
- **7.2.4.4** Participants will then be taken to the CRC bathroom and will be asked to provide a urine sample.
 - 7.2.4.4.1 A pregnancy test will be completed for women of childbearing potential.
 - **7.2.4.4.2** Participants will complete an exhaled carbon monoxide reading.

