COVID screening questions (day prior to visit)	x			Х			х			
Screening Questions	x									
Daily Cigarette and E-cig Use Diary	x	х	x	х	X	Х	х			
Past 7 day Cig and E-cig use								X	Х	
Other Tobacco Use	X	X	Х	Х	X	Х	X	X		
E-cig Patterns of Use and Log		X	Х	Х	X	Х	X	X		
Concomitant medications	X	X	Х	Х	X	Х	X	X		
Medical History	x	ĺ								
Cigarette Details	x									
Adverse events	X	X	Х	Х	X	Х	Х	X		
Demographics (Including Social Determinants of Health (SDOH))	x									
Tobacco use history	x									
Importance/Confidence to Quit	Х			Х		ľ	X	X		
NIDA drug screener (past 3 months)	x									
Environmental tobacco smoke	x			X			X			
Cigarette/E-cig perceived health risk	x			X						
E-cig Perceived Benefits and Harms	x									
Cigarette and E-cig Liking and Evaluation scales	x			X			x	x		х
Study Product Side Effects questionnaire		x	x	X	x	Х	x	x		х
Cigarette dependence (HONC, FTND, PSCDI)	x			X			x	x		
E-cig Dependence (Penn State E-cig DI)				X			x	x		
Questionnaire smoking urges	X	X	Х	Х	X	Х	X	X		х
Minnesota withdrawal scale	X	Х	X	Х	X	Х	Х	X		х
Audit-C	x						X			
CES-D	X			Х			Х			
Kessler K6	Х			Х			X			
Perceived stress scale	X			Х			X			

				0.	00100000	510
Clinical COPD questionnaire (CCQ)	X	X	X			
PROMIS Sleep Disturbance & Impact	x	X	X			
Interheart and WI Prepare	X		X			
Real World E-cig Use				Х		
Interview					Х	
Biomeasures/Procedures						
Weight	X	X	X			
Height	X					
Exhaled CO	X	X	X			x
Blood pressure/pulse	X	X	X			
Pulmonary function test (FEV1, FVC, PEF, FEF25, FEF75, FEF25-75, FET)	x	x	x			
Urine sample (NNAL, CYMA, MHBMA3, 3HPMA,8- isoprostanes, creatinine, cotinine)	x	x	x			
Holter EKG test (10 minutes)	X		X			
Pregnancy test	x	X	X			
Product use procedure			1			v

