- Baseline cigarette perceived health rick score
- E-cig Perceived risk/Perceptions of e-cig risks (from screener)
- Baseline CESD
- Baseline Kessler 6
- Baseline perceived stress
- Baseline COPD questionnaire
- Baseline interheart
- Importance and confidence to quit

Same strategy will be used for withdrawal items on the MNWS and scores on ratings of cigarette craving. The analysis will be conducted for the values of these variables at week 3, however.

Cigarette Abstainers Subgroup Analysis

In addition to the intent-to-treat analysis, additional analysis on subgroup of regular cigarette abstainers only will be conducted. By design, this subgroup will only consist of Switching Phase Completers (still in the study at the time of V3) who have successfully abstained from cigarette and other tobacco use (except e-cigs) from 1 week prior to V2 consistently and consecutively until V3. Therefore, this subgroup would be defined as 'quit' for at least 4 weeks. Participants in this sub-group must also have an exhaled CO < 6 ppm at both V2 and V3. Based on our previous data, we believe that 40% of the nicotine e-cig group (84 x .40 = roughly 33 participants) and 20% of the placebo e-cig group (84 x .20 = roughly 16 participants) will be classified as abstainers. For this relatively small subgroup, we shall only model the dependence of the outcome measures at week 6 on the two treatment arms while controlling for the baseline value of the outcome variable. No elaborate adjustment of other covariates will be included.

Aim 3: The proportions of subjects who will try to abstain from cigarettes and who will continue to use an e-cig at week 10 will be compared between the two arms using Fisher's exact test. Switching Phase dropouts will be treated as 'non-abstainers' from cigarettes under the 'worst case-scenario' assumption. A supplementary logistic regression will also be conducted to explore their dependence on demographic variables in addition to the two treatment arms.

Multiple imputation for missing values

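### Withdrawal and craving are hypothesised and defined as endpoints at week 1, but section 8.3 compares the arms on them at week 3 and plans no week-1 comparison

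*Combined protocol and SAP*

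**What the plan says.** Section 1.1.2.2 predicts that the nicotine arm, compared with the zero-nicotine arm after adjustment for baseline, will have a lower MNWS withdrawal total and "lower mean scores on ratings of cigarette craving, during the first week of the trial". Section 1.3 lists the matching secondary endpoint as "nicotine withdrawal and cravings, measured on the MNWS, at 1 week controlling for baseline".

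Section 8.3 describes the Aim 2 regressions of week-6 outcomes on arm, first with the baseline value and then with further covariates. It extends the same strategy to the MNWS withdrawal items and the craving ratings, and adds: "The analysis will be conducted for the values of these variables at week 3, however". It gives no reason for that choice.

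On timing, section 7.2.2 tells participants to "start using their assigned e-cig product beginning the next morning". Section 7.2.3 sets "Phone Contact #1 (Day 7 ± 7 days) and Phone Contact #2 (Day 14 ± 7 days"), and section 7.2.4 sets "Visit 2 (Day 21 ± 7 days"). The Time and Events Table marks the row "Minnesota withdrawal scale", and the smoking-urges questionnaire, at baseline and at every contact through Phone Contact #5. Phone Contact #1 at week 1 is among them.

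**The concern.** Two separate statements in the protocol, one a hypothesis and one an endpoint, agree on week 1. The analysis section disagrees with both, and nothing reconciles them. An analyst who follows 8.3 exactly would produce a comparison at about three weeks and no planned test of the first-week claim.

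Two things are at stake. A Visit 2 result could be reported as if it answered a question about the first days after switching. In addition, the scales are scored at several contacts, so an unresolved conflict leaves room to choose the time point once results are known.

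**Working it through.** The plan gives no figure for this point to reproduce. The check compares windows and then goes through each analysis in 8.3.

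**Windows** (sections 7.2.2, 7.2.3 and 7.2.4; Visit 1 is Day 0)

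- First week: product use starts the morning after Visit 1, so Days 1 to 7.
- Visit 2: 21 − 7 = Day 14 to 21 + 7 = Day 28. None of these days lies in Days 1 to 7. The earliest is 14 − 7 = 7 days after the first week ends, and the nominal day is 21 − 7 = 14 days after.
- Phone Contact #1: 7 − 7 = Day 0 to 7 + 7 = Day 14. Section 7.2.3 also says that "no visits (in person or phone), will occur on the same day", which rules out Day 0 and leaves Days 1 to 14.
- Phone Contact #2: 14 − 7 = Day 7 to 14 + 7 = Day 21. The two phone windows overlap on Days 7 to 14.

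No permitted timing of Visit 2 can therefore supply a first-week score. Phone Contact #1 can, but its own window runs past Day 7 and overlaps the next contact.

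**Is there a week-1 comparison between arms anywhere in 8.3?**

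| Analysis in 8.3 | Time | Compares arms at week 1? |
|---|---|---|
| Summary statistics | each visit | No; descriptive only, and covers week 1 only if phone contacts count as visits |
| Aim 1 change | to week 6 | No; run within each arm |
| Aim 1 mixed model | Visits 1, 2 and 3 | No; phone contacts not included |
| Aim 2 regressions, health markers | week 6 | No |
| Aim 2 regressions, MNWS and craving | week 3 | No |
| Abstainer subgroup regressions | week 6 | No |
| Aim 3 | week 10 | No |

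The Aim 1 text speaks of change starting from week 1. Even read literally, that is a within-arm estimate and does not compare the arms.

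**Would changing the week number be enough?** Not quite. The Aim 2 analysis set requires outcome data at Visit 2 or Visit 3. Applied to a week-1 outcome, that condition would make inclusion depend on later attendance. If week 3 is kept, the difficulty is different. The specific missing-value rules in 8.3 work towards a Visit 3 result: with Visit 2 missing and Visit 3 present, the table uses Visit 3 directly, and for a dropout before Visit 2 the carried value goes to Visit 3. Neither says what the Visit 2 outcome should be.

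**The case against.** The best defence is that week 3 is a leftover label. Other visit labels are stale: section 8.2 calls the last in-person visit Visit 4, section 7.4.5 puts randomisation at Visit 2, and the missing-value text in 8.3 refers to a Visit 2 baseline. This is plausible, and the documents cannot settle it. It explains the conflict without removing it, because the current schedule makes week 3 Day 21.

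It can also be said that little is lost: the week-1 scores are collected, they may be summarised, and only a secondary hypothesis is involved. That stands, and it limits the weight of the point.

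A reader might infer more than the text supports in three ways.

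- **That week 3 is the only time the arms are compared on these outcomes.** The abstainer regressions at week 6 do not name their outcomes, and the text does not say whether the mixed model has an arm term. Either might include MNWS or craving. Neither reaches week 1.
- **That week-1 scores of early dropouts would be overwritten with baseline values.** The carry-forward rule fills a missing Visit 3 value. Nothing tells the analyst to replace an observed Phone Contact #1 score.
- **That a missing Visit 2 value has no rule at all.** Section 8.3 names multiple imputation as its basic tool and excludes participants who stay in the trial but have neither Visit 2 nor Visit 3 data. The gap is narrower: Visit 2 missing with Visit 3 present, and early dropouts.

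**Conclusion.** The point holds for the time-point conflict. As written, hypothesis 1.1.2.2 and the matching endpoint in 1.3 are not tested between arms at week 1. The regressions that name these outcomes use Visit 2, nominally 14 days after the first week ends and at the earliest 7 days after. Week-1 scores receive summary statistics at most.

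The size is one secondary hypothesis covering withdrawal and craving. The primary endpoint, NNAL at 6 weeks, and its power statement in 8.2 are unaffected. The conclusion assumes that week 3 means what the Time and Events Table says, Visit 2 at Day 21, and that the first week is counted from the start of product use. It does not depend on which time point the sponsor intended. It should be fixed, because an analysis that follows the plan would not answer the question the protocol asks.

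**What to change.** Before unblinding, and without sight of outcomes by arm, settle one time point for 1.1.2.2, 1.3 and 8.3.

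**If week 1 stands**, revise 8.3 to:

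1. regress the Phone Contact #1 score on arm, adjusted for the Visit 1 value;
2. include all randomised participants who have a Phone Contact #1 score, without requiring Visit 2 or Visit 3 data;
3. state how contacts are assigned to week 1 (for example by contact number or by actual day), because the windows of Phone Contacts #1 and #2 overlap on Days 7 to 14;
4. label the week-3 regression as supportive.

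**If week 3 is intended**, amend 1.1.2.2 and 1.3 to say so. Add to 8.3 how a missing Visit 2 value is handled when Visit 3 is present and when the participant dropped out early.

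The cost is one revised paragraph in 8.3 or, if week 3 is kept, matching edits to 1.1.2.2 and 1.3 with a short missing-data rule. The scales are already collected at both time points, so no new data are needed.

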- 7.2.5 Switching Phase Phone Contact #3 (Day 28 ±7 days) and Phone Contact #4 (Day 35 ± 7 days) During each phone contact, daily study product and cigarette use will be collected, adverse events or changes to concomitant medications will be documented, and participants will be asked to verbally answer the measures indicated in the Time and Events Table during the phone call. Participants' answers will be entered directly into REDCap by the researcher at the time of the call. Participants will also be provided with advice/encouragement to remain abstinent from cigarettes. Participant's compensation for completing the phone call will be added to their Greenphire ClinCard.

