7.2.6 Switching Phase – Visit 3 (Day 42 -7/+14 days)

The following procedures will be completed in a private clinic space in the Clinical Research Center. Participants and researchers will be wearing appropriate PPE at all times, except for noted measures where the participant will need to remove their mask (when COVID protocols apply).

Prior to the visit:

7.2.6.1 Participants will be provided with instructions to complete measures via a home computer/smart phone (see table of measures). A link to the surveys in REDCap will be sent to the participant's email address or phone the day of the clinic visit. Participants will be instructed to complete all questionnaires within 24 hours. Participants unable to complete the questionnaires at home via a computer/smart phone will be called by the researchers to complete the questionnaires.

(Part A): Participant Check-In

- **7.2.6.2** The following measures will be completed:
 - **7.2.6.2.1** Adverse events will be documented, and any concomitant medication changes will be recorded.

- **7.2.6.2.2** The cigarette and study product use diaries will be collected by the researcher and entered into the Daily Cigarette and E-cig Use Diary Log in Redcap. Participants will stop using the diaries at this point of the study forward.
- **7.2.6.2.3** Use of other tobacco will be assessed via the Other Tobacco Use form.
- **7.2.6.2.4** All used and unused e-cig pods will be collected by the researcher for review. Participants will then be able to retain some of the unused pods based on their usage.
- **7.2.6.2.5** Participants will be encouraged to remain abstinent from cigarettes.
- **7.2.6.2.6** Participants will also verbally be provided with information regarding how they can purchase their own e-cig devices and products, similar to the one used in the study. Participants will be instructed to purchase e-liquid from reputable companies and to not buy from unknown or illicit sources.

(Part B): Completion of Biomeasures

- **7.2.6.3** The participant will then leave the clinic space to have their blood pressure and weight measured.
- **7.2.6.4** Participants will then be taken to the CRC bathroom and will be asked to provide a urine sample.
 - **7.2.6.4.1** A pregnancy test for women of child-bearing age will be completed.
- **7.2.6.5** The participants will return to the clinic space to completed the 10 minute Holter EKG.
- 7.2.6.6 Participants will complete an exhaled carbon monoxide reading.

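### The abstainer subgroup is labelled quit for at least 4 weeks, but the visit windows let its rule require as little as 2 weeks, and its arm contrast is not marked as non-randomized

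*Combined protocol and SAP*

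**What the plan says.** The Cigarette Abstainers Subgroup Analysis in 8.3 is additional to the modified intent-to-treat analysis. Members must still be in the study at Visit 3, must have avoided cigarettes and other tobacco (e-cigarettes excepted) "from 1 week prior to V2 consistently and consecutively until V3", and must have exhaled CO below 6 ppm at both visits. From this the plan infers: "Therefore, this subgroup would be defined as 'quit' for at least 4 weeks".

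The visit dates come from section 7.2:

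- 7.2.4: "Visit 2 (Day 21 ± 7 days"), that is, Day 14 to 28.
- 7.2.6: "Visit 3 (Day 42 -7/+14 days"), that is, Day 35 to 56.
- 7.2.5, between these visits: "Phone Contact #3 (Day 28 ±7 days) and Phone Contact #4 (Day 35 ± 7 days").
- 7.2.3, the only spacing rule found: "While visit windows were extended to allow the participant flexibility, no visits (in person or phone), will occur on the same day".

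The plan expects 40% of the nicotine group (roughly 33 of 84) and "20% of the placebo e-cig group (84 x .20 = roughly 16 participants) will be classified as abstainers". For this group, it says, "we shall only model the dependence of the outcome measures at week 6 on the two treatment arms while controlling for the baseline value". No further covariates enter the model.

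**The concern.** There are two separate problems.

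**The label.** The 4-week figure is presented as following from the rule and as a minimum. It matches the nominal schedule exactly, with no slack, while the visits may move in either direction. A report that follows the text could describe as 4-week quitters people who were held to a 2- or 3-week requirement.

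**The arm contrast.** Completing to Visit 3, abstaining and having a low CO are all determined after randomization. Aim 2 hypothesizes that nicotine facilitates switching, and the planning figures differ twofold between arms. The nicotine-arm and placebo-arm abstainers may therefore be different kinds of smoker. Adjusting for the baseline value of one outcome does not restore comparability. Without a caveat, the contrast could be reported as a randomized effect of nicotine among people who quit.

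**Working it through.** **Inputs.** Rule, CO criterion and expected membership: 8.3. Visit 2 window, Day 14 to 28: 7.2.4. Visit 3 window, Day 35 to 56: 7.2.6. Phone Contact #3, Day 21 to 35, and #4, Day 28 to 42: 7.2.5. No same-day contacts: 7.2.3.

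**Formula.** Required run = V3 − (V2 − 7) = (V3 − V2) + 7 days.

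**The plan's own figure.** On nominal dates, (42 − 21) + 7 = 28 days. Four weeks is reproduced.

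**As a minimum.** A run of at least 28 days needs V3 − V2 ≥ 21. Within the windows:

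| Visit 2 | Visit 3 | Required run |
|---|---|---|
| Day 21 | Day 42 | 28 days |
| Day 28 | Day 42 | (42 − 28) + 7 = 21 days |
| Day 21 | Day 35 | (35 − 21) + 7 = 21 days |
| Day 28 | Day 35 | (35 − 28) + 7 = 14 days |

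One displaced visit is enough. With Visit 3 on Day 42, any Visit 2 on Day 22 to 28 gives 27 down to 21 days. With Visit 2 on Day 21, any Visit 3 on Day 35 to 41 gives 21 up to 27 days. With Visit 2 on Day 28, Visit 3 must fall on Day 49 or later to reach 28.

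**How much of the permitted calendar this covers.** There are 15 × 22 = 330 permitted date pairs. The run is below 28 days when V3 < V2 + 21. That excludes no Visit 3 day when V2 = 14, one when V2 = 15, and so on up to fourteen when V2 = 28: 0 + 1 + … + 14 = 105 pairs (32%). The other 225 satisfy the label.

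**Do other rules prevent the short case?** Visit 2 on Day 28, Phone #3 on Day 29, Phone #4 on Day 30 and Visit 3 on Day 35 are all in window and on different days, so the spacing rule allows it. CO is required at two visits only, so it sets no duration. No minimum gap between visits and no minimum count of abstinent days was found.

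**Arm contrast.** On the plan's figures, with 84 completers per arm, 0.40 of nicotine completers and 0.20 of placebo completers qualify. Completion is 84/120 = 0.70 in each arm, so per randomized participant this is 0.28 against 0.14. At least (0.28 − 0.14)/0.28 = 50% of nicotine-arm members would then not have qualified on placebo. This shows that the two groups need not be alike. It does not say how far any estimate would move.

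**The case against.** The strongest reply has three parts.

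**Most permitted schedules meet the label.** Of the 330 pairs, 225 (68%) require 28 days or more. The Visit 3 window extends further late than early, and the 14-day figure comes from a single corner. This stands as a limit on size: only runs of 14 to 27 days are at fault. It does not rescue the label, which states a minimum, and ordinary in-window shifts of one visit already break it.

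**The required run is not the achieved duration.** Switching starts the morning after Visit 1, so many members may have abstained longer than the rule asks. This stands. A reader might infer that some members were quit for only two weeks, or that 32% of them are mislabelled. The documents support neither. The 32% is a count of permitted dates, and neither actual visit timing nor actual abstinence is known.

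**The second part is a matter of reporting.** The plan names modified intent-to-treat as its primary framework, calls this analysis additional, states the criteria openly and publishes the unequal expected membership. It nowhere claims a randomized effect among quitters. That is fair. But calling an analysis additional gives its rank, not the loss of randomization, and one sentence would close the gap.

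**Conclusion.** Both parts hold, at low severity. The rule guarantees four weeks only when Visit 3 is at least 21 days after Visit 2. Within the permitted windows it can require as little as 14 days, so the stated minimum does not follow. The result rests only on the rule and windows as written and assumes visits within window. The number of participants affected cannot be derived from the documents.

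The within-abstainer contrast is a comparison of groups selected after randomization, and the plan should say so. A reader might go further and infer that the contrast is biased in a particular direction or by a known amount. The documents give nothing from which to compute either. Nor does the point reach the primary modified intent-to-treat analysis or the sample size, which do not use this subgroup.

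**What to change.** 1. **Label.** Replace the 4-week statement in 8.3 with: abstinent from 1 week before V2 through V3 (nominally 4 weeks; the visit windows permit a required run as short as 2 weeks). Subgroup membership does not change. Report actual cigarette-abstinence duration by arm from the daily diary, whose totals are entered for all study days up to Visit 3 (7.2.10).
2. **Optional, if a true 4-week group is wanted.** Add a sensitivity analysis limited to members with at least 28 diary-documented cigarette-free days ending at Visit 3. It is attainable on every permitted date: the earliest start is 35 − 28 = Day 7, after switching has begun. The price is a group that can only be as large as or smaller than the expected 33 versus 16, defined by self-report.
3. **Arm contrast.** State that it is descriptive and non-randomized. Tabulate baseline cigarettes per day, PSCDI and NNAL by arm among members; all three are already on the covariate list in 8.3.

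The cost is SAP wording, one small table and a duration summary. No new data are collected.
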